**FORM: Application for Human Research**

| NUMBER | FORM DATE | PAGE |
|--------|-----------|----------|
| F200 | 02/2014 | 36 of 44 |

1244 LEDs could lead to more severe changes in vision such as photoretinitis, a condition that is most
1245 commonly associated with looking for too long at very bright light sources such as snow on a bright
1246 sunny day or looking at the sun during an eclipse. Such a condition could lead to temporary or long-term
1247 vision problems. As individuals may differ in sensitivity to light, some subjects may experience eye
1248 fatigue or irritation during the use of the light exposure device. If subjects notice any unusual sensations
1249 or discomforts, they are advised to discontinue use and to contact the Principal Investigator immediately.
1250

1251 Thus, to minimize risk, subjects will be instructed via the following for the goLITE Blu:
1252

1253 **NOTE: DO NOT STARE DIRECTLY AT THE LIGHTS ON THE LED PANEL.**
1254 **IT IS SUFFICIENT THAT THE LIGHT REACHES YOUR EYES DIRECTLY FROM THE**
1255 **SIDE.**

1256 There is the potential for skin irritation due to the heart rate monitor leads or wearing the
1257 actiwatch. This can be alleviated with use of lotions and/or creams.
1258

1260 **9) Potential benefits to subjects and/or society**

1261 It is not anticipated that subjects will derive direct benefit from participation in the proposed
1262 study. However, it is anticipated that findings from this study will help to advance scientific and medical
1263 understanding of treatment of PTSD and sleep disorders. The study will provide basic scientific
1264 information about the effects of short wavelength light on sleep patterns and potential treatment of PTSD.
1265 Such information may improve the ability to treat sleep disorders and cognitive performance among
1266 patients with PTSD.
1267

1268 Incidental MRI findings:

1269 Study assessments (labs, MRI scans, psychological assessments, etc.) are not intended to provide medical
1270 benefit. Personnel involved conducting this study may not be trained or licensed to clinically review lab
1271 findings, MRI images, etc. If study personnel notice something irregular in subjects' study information,
1272 the investigator may provide de-identified reports or images to a licensed physician, radiologists, or other
1273 qualified practitioner for further review. In the unlikely case that such a qualified clinician determines a
1274 finding to be an irregularity, subjects will be advised to consult their primary care physician. Subjects
1275 may be provided copies of their study information or MRI images for this purpose, but this medical
1276 consultation will be on subjects' own time and at their cost. If subjects are provided a copy of their study
1277 information, we make no promises as to the clinical value of the data. The University of Arizona and its
1278 employees have no funds set aside for the payment of treatment expenses that may arise from subjects
1279 volunteering for an MRI scan.

1280 There may be instances in which an abnormality exists but is not identified in our analyses. Our
1281 team is not trained in clinically diagnosing issues pertaining to abnormalities found in the collected data.
1282 Further, our data analyses are not intended to treat, diagnose, or replace the expertise of a medical doctor
1283 or a medical diagnosis. As such, the University of Arizona and its employees are not responsible for

**FORM: Application for Human Research**

| NUMBER | FORM DATE | PAGE |
|--------|-----------|----------|
| F200 | 02/2014 | 37 of 44 |

1284 abnormalities that go undetected through participation in these research activities and subjects will be told
1285 that they should not rely on our data or analyses to reveal abnormalities.
1286

1287 **10) Provisions to protect the privacy of subjects and the confidentiality of data**

1288 Collected data are computerized. A unique study-specific ID number is assigned to each subject
1289 and used for identification purposes. A separate password-protected data file, stored on a stand-alone PC,
1290 maintains the ID number and identifying information for each participant. Only the PI and Project
1291 Coordinator have access to that file.

1292 Data collected will be entered into REDCap in de-identified format. Subjects' identities will be linked
1293 via a coded/subject ID. REDCap requires authorized users to enter a username and password unique to
1294 each study staff member.

1295 Study data will be maintained on secure servers maintained by University of Arizona College of
1296 Medicine IT, accessible only through secure UA networks by UA-affiliated computers. Only authorized
1297 researchers associated with this project will be given access via a unique medadmin username and
1298 password.

1299 All information regarding experimental subjects are kept in a locked file cabinet in the University
1300 of Arizona Department of Psychiatry. The signed consent forms are stored separately from the research
1301 data in a locked file cabinet in the Department of Psychiatry. Any study forms that contain personally
1302 identifying information for our participants (e.g., signed consent forms, payment information) are kept
1303 separately from research records and data in separate locked filing cabinets in the Department of
1304 Psychiatry. All subject voice recordings will be used to verify that the study team collected complete
1305 responses and will be verified and deleted the same day they are collected. These recordings will only be
1306 linked to subject IDs during that period.

1307 The Imaging Center will be provided with Subject ID numbers only. MRI Records are kept in a
1308 locked office. Subject identifiable information is not used for research data. HIPAA requirements will be
1309 followed to protect subject confidentiality.

1310 For subjects who agree, their information will be saved for future use to allow possible contact for
1311 other studies conducted by the PI.

1312 A final study report will be made available to the sponsor, the Department of Defense (DoD). Only
1313 non-identifiable data will be shared. DoD maintains a secure file transfer system, "DoD SAFE," which
1314 can be used to securely transfer study information to the sponsor.

1315 Research data will be stored in a secure area for a period of 6 years following the conclusion of the
1316 study. All data and links will be destroyed as soon as possible.

1317 **11) Cost to subjects**

1318 There are no costs to subjects, except for their time.
1319

1320 **12) Subject compensation**

1321 Potential subjects who complete pre-screening surveys (*Recruitment Survey.pdf*) through
1322 crowdsourcing websites will be compensated in line with the specific site's payment policy (e.g., Amazon

FORM: Application for Human Research

| NUMBER | FORM DATE | PAGE |
|--------|-----------|----------|
| F200 | 02/2014 | 38 of 44 |

1323 Mechanical Turk will pay \$0.60 after the survey is completed, a rate of \$0.12 per min in compliance with
1324 research guidelines for fair wages within the MTurk community, with a predetermined 5-minute effort
1325 allotted).

1326 Subjects will receive \$1200 for completion of all three study sessions, successful adherence to
1327 daily light exposure treatment, and compliance with all study procedures and proper use of all study
1328 equipment. This payment is also intended to cover all transportation expenses to and from the study site.

1329 If subjects choose to withdraw from the study prematurely or are disqualified for any reason,
1330 subjects will be compensated according to the following schedule for the time subjects were undergoing
1331 scanning and testing:

- 1333 • Discontinuation during or following the initial intake visit: \$75 (\$25/hour, 3 hours max for day),
1334 following return and adherence of all study-related tasks and equipment.
- 1335 • Discontinuation before the end of second visit: \$17.05/hour, up to a maximum of 8.5 hours and
1336 \$145 for the day (i.e., max = \$220 total for both days), following return and adherence of all
1337 study-related tasks and equipment.
- 1338 • Discontinuation any time during the 6-week light exposure period: \$220 maximum total payment,
1339 following return and adherence to all study-related tasks and equipment.
- 1340 • Fully compliant participants will receive \$980 for completion of all light exposure sessions, proper
1341 use of light meter, and completion of all research activities during the final visit. Payment to
1342 participants who discontinue their participation between the second visit and the final visit is
1343 variable depending on days of light exposure missed:

- 1344 ○ 1 day missed: Maximum total payment \$1200
- 1345 ○ 2 days missed: Maximum total payment of \$1195
- 1346 ○ 3 days missed: Maximum total payment of \$1190
- 1347 ○ 4 days missed: Maximum total payment of \$1180
- 1348 ○ 5 days missed: Maximum total payment of \$1160
- 1349 ○ 6 days missed: Maximum total payment of \$1120
- 1350 ○ 7 days missed: Maximum total payment of \$1040
- 1351 ○ 8 days missed: Maximum total payment of \$880
- 1352 ○ 9 days missed: Maximum total payment of \$560
- 1353 ○ More than 9 days missed: \$220 maximum from completion of first 2 visits

1354
1355 Payment cannot be rendered until all study-related equipment has been returned. In order to be
1356 compensated for participation in this study, subjects must be a U.S. citizen or other person legally entitled
1357 to earn money in the U.S. By law, payments to subjects may be considered taxable income.

1358
1359 **If the participant is an active duty military personnel**, the participant is not eligible to receive
1360 compensation for time spent completing assessments while they are "on duty". In accordance with Title
1361 24 United States Code 30, active duty military personnel must be on leave status during each of the three
1362 assessment sessions in order to be compensated. If the participant is on active duty, **it is their**
1363 **responsibility** to ensure that they have completed the appropriate paperwork for leave and obtained the

**FORM: Application for Human Research**

| NUMBER | FORM DATE | PAGE |
|--------|-----------|----------|
| F200 | 02/2014 | 39 of 44 |

1364 necessary permissions to allow them to participate in this study. If the participant is on leave status, they
1365 will be compensated for the 3 assessment sessions according to the schedule listed above.

1366
1367 The necessary information to capture receipt of subject payment will be collected via the Subject
1368 Payment Form.

1369 Method of payment: Participants will be paid in cash or check. Patients may need to complete a W-9
1370 (IRS Request for Taxpayer Identification Number and Certification) in the Psychiatry business office
1371 depending on the amount of compensation being provided for this study and their extent of involvement.

1372
1373
1374 **13) Medical care and compensation for injury**

1375 Subjects will be offered the care needed to treat any injury that directly results from taking part in
1376 this research study. We reserve the right to bill their insurance company or other third parties, if
1377 appropriate, for the care they get for the injury. We will try to have these costs paid for, but subjects may
1378 be responsible for some of them.

1379 Injuries sometimes happen in research even when no one is at fault. There are no plans to pay
1380 subjects or give them other compensation for an injury, should one occur. However, they are not giving
1381 up any of their legal rights by signing this form.

1382 If subjects think they have been injured or have experienced a medical problem as a result of
1383 taking part in this research study, they are to tell the person in charge of this study as soon as possible.

1384 Siemens will pay for the actual cost of reasonable and necessary medical treatment if a study subject
1385 is injured during the Trial, to the extent the injury is a direct result of the proper performance of study
1386 procedures that:

1387
1388
1389
1390
1391
1392

- are pursuant to the study plan,
- are not standard of care, unless included in the study plan,
- would not otherwise have been performed but for a subject's participation in the study,
- are not a result of the negligence or willful misconduct of UA personnel, and
- are not the result of normal progression of a study subject's underlying disease.

1393
1394 **14) Monitoring the data for subject safety**

1395 The principal investigator will oversee the collection, maintenance, and analysis of all data. The
1396 UA HSPP will be contacted immediately in the case of unexpected adverse events. This is not a treatment
1397 trial. [name], is director of the sleep laboratory and oversees collection of sleep PSG and
1398 actigraphy data. [name], is an expert in PTSD and contributes to the design, development,
1399 analysis and interpretation of data. In addition to [name], in the event a subject should report suicidal
1400 ideation and she is not available for consultation/assessment, [name] PhD, or another qualified
1401 clinician, will provide assessment to promote the well-being of the subject. [name], is an
expert in the development and application of novel MRI technologies and will assist with collection of

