 175 to compare an active treatment device with wavelengths peaking at 469 nm (blue) versus an identical
 176 placebo device fitted with amber colored diodes (see Figure 1). Thus, this study will be the first, large
 177 placebo controlled study examining the effectiveness and neuroimaging correlates of BLT in PTSD.

Figure 1. Blue Light (BL) and amber placebo light (PL) devices

178

 179 **A. 3. Preliminary Data**

180 Our group has a long history of using functional
 181 neuroimaging techniques to study PTSD. Using a
 182 paradigm known as the Masked Affect Task (MAT),
 183 our lab reported that combat exposed veterans with
 184 PTSD showed exaggerated amygdala responses to
 185 fear-related facial stimuli perceived below the
 186 threshold of conscious awareness when compared to
 187 combat exposed veterans without PTSD [27]. We
 188 have now collected pilot data on 65 participants,
 189 including 14 individuals with PTSD, 14 individuals
 190 with panic disorder, and 15 participants with simple
 191 phobias using this same paradigm. As evident in the
 192 figure, compared to healthy controls or other anxiety
 193 groups viewing masked fearful faces, patients with
 194 PTSD showed greater activation within the
 195 amygdala, one of the primary brain structures
 196 involved in the assessment of threat. PTSD subjects
 197 also showed reduced activation within the ventromedial prefrontal
 198 cortex relative to healthy controls. This suggests that the
 199 hyperarousal and exaggerated startle reflexes associated with PTSD
 200 may be partly the result of abnormal responses in the amygdala. At
 201 present, no neuroimaging studies have yet examined the role of
 202 sleep in this process. However, recent data from Yoo and
 203 colleagues suggests that loss of normal sleep is associated with
 204 reduced functional connectivity between the VMPFC and the
 205 amygdala, suggesting that sleep loss may reduce the ability of the
 206 prefrontal cortex to regulate the emotional responses of the
 207 amygdala [81]. We have also conducted an fMRI study showing that reduced sleep is associated with
 208 altered functional connectivity between the VMPFC and amygdala, and the strength of such connectivity
 209 is directly related to the severity of symptoms of anxiety, depression, and reduced emotional functioning
 210 [82]. Our preliminary studies of cognitive functioning during sleep deprivation support the prefrontal-

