**FORM: Application for Human Research**

| NUMBER | FORM DATE | PAGE |
|--------|-----------|----------|
| F200 | 02/2014 | 16 of 44 |

443 burdensome than it appears, as over 30 participants have already successfully completed this same
444 protocol in our pilot study of mild traumatic brain injury without any complaints or discontinuations due
445 to excessive burden. Finally, the **potential impact** of this study is high because of the capability of
446 transitioning the research to direct clinical application almost immediately. If the BL treatment is
447 demonstrated as effective, this approach would be readily available for nearly immediate large-scale
448 implementation, as the devices have been widely used for years in other contexts, are already safety
449 tested, and commercially available from several manufacturers for a very low cost. Thus, the impact of
450 this research on treating PTSD would be high and immediate.

451

452 **3) Setting of the Human Research**

453 This study requires three visits including an initial assessment and two testing/scanning sessions
454 separated by six-weeks of daily light exposure treatment at home.

455 For the initial assessment and the baseline testing session, subjects will be seen at the Lab of Dr.
456 [name] in the University of Arizona Department of Psychiatry. There, subjects will complete personality
457 assessments, a comprehensive cognitive assessment battery, and several tests of motor functioning.

458
459 **Magnetic Resonance Imaging (MRI) Procedures:** The data collection will occur at the research-
460 dedicated University of Arizona scanner facility that houses a new 3 Tesla magnet (see Equipment for
461 description). For functional neuroimaging, audio and visual stimulus presentation equipment is available
462 through the Resonance Technologies headphone/goggle system or high-definition MRI-compatible LCD-
463 display (viewed through a mirror in the head cage). An fMRI compatible EEG system including caps,
464 cabling, and pre-amplifier is integrated with this space (see Equipment for description). Scanner data are
465 transferred securely to a RAID storage system for subsequent transfer to PI laboratories. Offline analysis
466 will take place in the Laboratory of PI [name].

467 In January 2013, the University of Arizona purchased a Siemens Magnetom TIM Skyra 3T that is
468 capable of high-resolution imaging capabilities. This whole-body 3.0T device will be configured with 48

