1231 or enclosed within an FDA or UofA HSPP approved MRI coil. The volunteer may be asked to interact
1232 with a peripheral system such as a button, joystick, or TV system before, during, or after the scan.

1233
1234 Although both light devices (placebo [PL] and blue light [BLT]) are safe to use (Sliney, 2009,
1235 2006; Apollo Health, 2009), we will minimize unnecessary direct exposure to the bright lights to reduce
1236 the possibility of discomfort or persistent visual symptoms. Although looking directly at the LEDs for
1237 brief periods is not known to be harmful, it is unnecessary and may lead to glare, eyestrain, or other
1238 irritating visual sensations that can be easily avoided by keeping the panel at an angle in the peripheral
1239 vision. It is sufficient that the light reaches the eyes indirectly from the side. Looking directly at the LEDs
1240 does not provide any additional benefit. Prolonged staring at the LEDs could lead to significant eye
1241 irritation, lingering afterimages, or other symptoms such as headaches. Although the light emissions of
1242 the device are well within safe limits and no problems have ever been reported, we want to minimize any
1243 risks or discomforts. While extremely unlikely, it is possible that prolonged continuous staring at the

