**FORM: Application for Human Research**

| NUMBER | FORM DATE | PAGE |
|--------|-----------|----------|
| F200 | 02/2014 | 40 of 44 |

1402 magnetic resonance spectroscopy imaging, analysis strategies, and statistical analysis of MRS and DTI
1403 data.

1404 Subjects may refuse to answer any questions that make them uncomfortable. In addition, subjects
1405 may terminate their participation in the study at any time. If significant psychopathology (e.g., threat of
1406 harm to self or others) is discovered at any time during or after a subject's visit, we will contact one of the
1407 psychiatrists on staff to determine the level of risk and establish a contract for safety. If the subject does
1408 not already have an established relationship with a psychiatrist, we will provide the appropriate referrals
1409 for psychiatric evaluation.

1410 Assessment of MRI scanning-related safety issues will occur at every scanning session by the
1411 study staff. Risks to subjects will be minimized by following standard MRI procedures. Individual scans
1412 will be aborted if any safety parameters are breached. If the safety issue involves the patient that cannot
1413 be eliminated within the time course of the study, their involvement in the study will be terminated. If the
1414 safety issue involves the scanner or the scanning environment, no further scans will be conducted from
1415 that point, until assurances are made that all safety parameters have returned to allowable limits.

1416 Female participants must have a negative pregnancy test before the MRI scan can be initiated. If
1417 the results of the pregnancy test are positive, one of the clinically trained study investigators will explain
1418 why the scan cannot be completed.

1419 No long-lasting physical or economic harm is anticipated during scanning. Every effort will be
1420 made to reassure the patient and minimize any such discomforts while scanning. Subjects will be offered
1421 and required to wear earplugs and/or earphones to minimize the scanner noise. Subjects will be able to
1422 converse with a staff member via a microphone and speaker system at all times during the scanning
1423 session. Subjects will be provided with an emergency button to indicate an immediate concern. Subjects
1424 may ask to have a scan stopped and discontinue participation in the study at any time.

1425 In case of an adverse event, the principal investigator will evaluate and report such events to the

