1426 UA HSPP per UA HSPP guidelines as well as report to HRPO per federal guidelines.

1427 The diagnostic assessment, MRI, and heart rate measures may reveal previously unidentified
1428 psychiatric disorders and/or brain or heart abnormalities the subject didn't know they had. If any
1429 abnormalities are identified, they will be provided with information about the finding and encouraged to
1430 follow up with their primary care physician. Subjects will be made aware that we are not providing
1431 psychiatric, neuroradiological, or other clinical services; only that we will let them know in the event that
1432 anything abnormal is noticed by the study team. We are unable to assume responsibility or offer
1433 compensation for related medical costs that they make as a result of being informed of an abnormal
1434 finding.

1435 There may be instances in which an abnormality exists but is not identified in our analyses. Our team
1436 is not trained in clinically diagnosing issues pertaining to abnormalities found in the collected data.
1437 Further, our data analyses are not intended to treat, diagnose, or replace the expertise of a medical doctor
1438 or a medical diagnosis. Thus, subjects will be aware that they should not rely on our analyses to reveal
1439 abnormalities in their data, and our lab claims no responsibility for abnormalities that go undetected
1440 during participation in any research related activities.

1441
1442

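### The light-related harms that the protocol lists have no described scheduled, solicited collection and no planned by-arm table, so tolerability would rest on spontaneous reports

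*Combined protocol and SAP*

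**What the plan says.** **Harms foreseen.** Section 8 (Risks to subjects) warns that prolonged staring at the LEDs could cause "irritation, lingering afterimages, or other symptoms such as headaches". It also names glare, eyestrain and eye fatigue and, as extremely unlikely, photoretinitis with temporary or lasting vision problems.

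**How they reach the team.** Section 8 says of participants who notice unusual sensations "or discomforts, they are advised to discontinue use and to contact the Principal Investigator immediately". Section 13 likewise asks those who think they were injured, or who have a medical problem, to tell the person in charge.

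**What happens next.** Section 14 says that the university's human-subjects office "will be contacted immediately in the case of unexpected adverse events. This is not a treatment" trial. Further on it adds: "In case of an adverse event, the principal investigator will evaluate and report such events to the" "UA HSPP per UA HSPP guidelines as well as report to HRPO per federal guidelines". That second rule is not limited to unexpected events.

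**Scheduled checks.** Section 14 specifies safety assessment at every MRI session. The consent part of Section 6 has staff ask about continued participation after each major study component and watch for visible difficulty with procedures.

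**Analysis.** Section D plans comparisons of sleep, mood, symptoms, cognition and imaging. It names no adverse-event or tolerability summary.

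**Purpose.** The Background calls this the first large "placebo controlled study examining the effectiveness and neuroimaging correlates of BLT in PTSD". The Lay Summary says that if the treatment is "demonstrated as effective, this approach would be readily available for nearly immediate large-scale" use.

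**The concern.** The protocol foresees specific, mostly mild symptoms from the intervention, yet the only capture it describes for them starts with the participant. Mild eye strain or headache is easily left unreported, and two features add to that.

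First, the same sentence that asks for contact advises the participant to stop using the light. Section 12 lowers the maximum payment as light days are missed. Someone with a bothersome symptom may therefore have a financial reason not to mention it.

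Second, the protocol already cites the absence of reported problems with the devices as reassurance. If this trial collects harms in the same way, it adds evidence of the same weak kind, while the Lay Summary looks ahead to rapid large-scale use.

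At stake are the early detection of visual symptoms that Section 8 wants to avoid, and a usable description of tolerability by arm. The two devices differ in stated irradiance (1.23 and 0.35 mW/cm²), so such a description would be informative.

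**Working it through.** The plan gives no figure for harms, so there is none to reproduce. The check is a reading of the text, followed by an illustration on assumed rates.

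**1. Is there a scheduled question about light symptoms?**

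| Place | What is visible | Covers light symptoms? |
|---|---|---|
| Section 8, light-device text | Participant stops use and contacts the investigator | Yes, participant-initiated |
| Section 13 | Participant reports injury or medical problem | Yes, participant-initiated |
| Section 14, scan safety | Staff assess at every scan | MRI only |
| Section 6, consent process | Staff ask about continuing | Not as described |
| Section 7, online diary | Sleep and timing of light use; staff contact after more than 48 hours without log-in | Not as described |
| Section 7, Visits 2 and 3 | Health questionnaire and day-of-scan questionnaire | Content not shown |
| Section 4, attachments | No side-effect form listed; a post-treatment day-of-scan form is listed | Content not shown |

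No visible text provides scheduled, solicited collection. The two questionnaires leave this open for visit days. Neither is described as used during the six weeks at home.

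**2. Payment.** Section 12 gives $1200 for completion, $1160 with 5 days missed, $560 with 9, and at most $220 with more than 9 or on discontinuing during treatment. The largest loss is 1200 − 220 = $980. One missed day costs nothing.

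**3. Effect of passive capture in one arm.** n = 45 is from Section 7. The incidence p and the share c of cases that become known are assumptions.

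- Expected reports = n × p × c
- Chance of no report = (1 − p × c)^n

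| p | c | Expected reports | Chance of none |
|---|---|---|---|
| 10% | 20% | 45 × 0.02 = 0.9 | 0.98^45 = 0.40 |
| 10% | 50% | 45 × 0.05 = 2.25 | 0.95^45 = 0.10 |
| 10% | 100% | 45 × 0.10 = 4.5 | 0.90^45 = 0.009 |
| 5% | 20% | 45 × 0.01 = 0.45 | 0.99^45 = 0.64 |
| 5% | 50% | 45 × 0.025 = 1.125 | 0.975^45 = 0.32 |
| 5% | 100% | 45 × 0.05 = 2.25 | 0.95^45 = 0.10 |

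**4. What zero reports would show.** With full capture, 0 of 45 gives a one-sided 95% upper bound of 1 − 0.05^(1/45) = 6.4%. With share c captured, that bound applies to p × c, so the bound on p is 6.4%/0.5 = 13% at half capture and 6.4%/0.2 = 32% at one fifth.

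**5. Comparison between arms.** Normal approximation for two proportions, 45 per arm, two-sided α = 0.05, the same capture share in both arms. For assumed true rates of 30% and 10%, power is 0.67 with full capture. It is 0.35 with half captured (15% and 5%) and 0.22 with 30% captured (9% and 3%). For 10% and 5% with full capture it is only about 0.15.

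**The case against.** The case on the other side is substantial, and several tempting readings fail.

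- **A reader might infer that only unexpected events are escalated.** They are not. Section 14 limits only the immediate contact to unexpected events. Its later rule covers adverse events generally, so an expected headache, once known, is evaluated and reported.
- **A reader might infer that the not-a-treatment-trial sentence causes the passive capture.** It does not. Who is told of an event is separate from how the event is found, and deleting the sentence would change nothing about ascertainment.
- **A reader might infer that capture is proven to depend wholly on volunteering.** The visible text cannot show this. The health questionnaire and the post-treatment day-of-scan form may ask about symptoms. Even so, a form at six weeks would not give timely detection and could miss people who stopped and did not return.
- **A reader might infer that the arms cannot be compared.** They can. Spontaneous reports, withdrawals and metered light use can all be tabulated by randomised arm. The comparison is unplanned and likely to be under-ascertained, not impossible.

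The protocol also says that the safety and efficacy of the device itself are not under test, that the devices have had ocular safety testing, and that severe harm is extremely unlikely. This is a fair argument against a large safety apparatus. It is weaker against asking about symptoms that the protocol itself lists.

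Finally, even complete capture would not give 45 per arm useful power for small differences. That stands, and it is why the fix is descriptive.

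**Conclusion.** The concern holds as a gap in ascertainment. The protocol lists light-related harms, describes only participant-initiated routes for learning of them, ties payment to continued light use, and plans no by-arm tolerability table. Any tolerability comparison would rest on spontaneous reports. It does not hold as a fault in escalation.

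The size is illustrative. On an assumed incidence of 5% to 10% and an assumed 20% to 50% of cases volunteered, the chance that a real harm leaves no record in an arm of 45 lies between 10% and 64%, against 0.9% to 10% if all cases are captured. The documents give neither incidence nor reporting share. Full capture under a checklist is a best case, and equal capture in both arms is also assumed. If the shares differed by arm, the comparison would be biased as well as weak.

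The conclusion would narrow if the unseen questionnaires already ask about these symptoms. The lack of described in-treatment questioning and of a planned table would remain. This should be changed, but it does not threaten the efficacy analysis.

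**What to change.** 1. Add a short fixed checklist of the symptoms that Section 8 already names to the existing online diary, and ask it at Visit 2 (baseline) and Visit 3, with identical wording in both arms. If the health or day-of-scan questionnaire already covers these items, cite it and add only what is missing.
2. State that staff review the answers during routine diary monitoring, which at present is described only as a check on log-ins.
3. Add to Section D one table of counts by randomised arm with confidence intervals, labelled as description and not as a powered test. Show withdrawals and metered light use beside it.
4. Separately, reconcile the Section 14 statement that this is not a treatment trial with the randomised, placebo-controlled effectiveness design in the Background and Section 7. This is a matter of consistency only.

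The cost is a few seconds of diary time, more minor events to log, and one table. Asking may itself prompt some symptom reports, but with the same wording this should act equally in both arms. The advice to participants, the treatment, the endpoints and the sample size are unchanged.
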